# 6.4. RETESTS, UNSCHEDULED VISITS AND EARLY TERMINATION DATA

In general, for by-visit summaries, data recorded at the nominal visit will be included in analysis. Unscheduled measurements will not be included in by-visit summaries, but will contribute to the worst case value where required (e.g., shift tables).

In the case of a retest (same visit number assigned), the latest available measurement for that visit will be used for by-visit summaries.

Subject data listings will present all available data: scheduled, unscheduled, retest, and ET visit data.

## 6.5. WINDOWING CONVENTIONS

There will be no visit windowing for this protocol. All data will be organized and analysed according to the scheduled times as outlined in the protocol and by the visit denoted on the electronic Case Report Form (eCRF). Early termination visit information will be handled as described in Section 6.3.

## **6.6. STATISTICAL TESTS**

All statistical tests of treatment effects will be performed at a 2 sided significance level of 0.05, unless otherwise stated. Confidence intervals will be 95%, unless otherwise specified in the description of the analyses.

For primary analysis and analysis of the key secondary endpoint, both unadjusted and adjusted p-values will be reported.

Document:	\\quintiles.net\Enterprise\Apps\sasdata\SASb\SAS\Noven\HP-		
	3070\XWA17541\Biostatistics\Documentation\SAP\Final 6\Noven HP-3070-GL-04 SAP text Final		
	6_18Jan2018.docx		
Author:	[name]	Version Number:	Final 6
		Version Date:	18Jan2018
Template No:	CS_TP_BS016 – Revision 3	Reference: 0	CS_WI_BS005

Effective Date: 01May2012

Copyright © 2012 Quintiles Transnational Corp. All rights reserved.

Noven Pharmaceuticals, Inc. STATISTICAL ANALYSIS PLAN: PROTOCOL HP-3070-GL-04 Page 18 of 50

## 6.7. COMMON CALCULATIONS

For quantitative measurements, change from baseline will be calculated as Test Value at Visit X - Baseline Value.

Continuous variables will be summarized by descriptive statistics (sample size [n], mean, standard deviation [SD], median, minimum, and maximum). Categorical variables will be summarized in frequency tables (n, frequencies, and percentages).

# 6.8. SOFTWARE VERSION

All analyses will be conducted using SAS® version 9.2 or higher.

Details for software to be used for model based analysis will be described in a standalone modeling and simulation plan.

# 7. STATISTICAL CONSIDERATIONS

# 7.1. ADJUSTMENTS FOR COVARIATES AND FACTORS TO BE INCLUDED IN ANALYSES

The following covariates and factors are used in the analyses. For details of their inclusion in the models, see the specific analysis section.

- Country
- Baseline value corresponding to the parameter being analyzed

# 7.2. MULTICENTER STUDIES

This study will be conducted by multiple investigators at multiple centers internationally. Randomization to treatment arms will be stratified by country. Country will be used as a factor in statistical analyses.

# 7.3. MISSING DATA

In the calculation of total and subscale scores, missing individual items used in the derivations of aggregate scores will be handled as described in the sections defining the corresponding variables, in accordance with a scoring manual for each scale.

Missing endpoint values in this study may result from patients discontinuing from the study prematurely or

	6 19 Jan 2019 docx		
	6_18Jan2018.00CX		
Author:	[name]	Version Number:	Final 6
		Version Date:	18Jan2018
Template No: CS_TP_BS016 – Revision 3		Reference: CS_WI_BS005	

Effective Date: 01May2012

Copyright © 2012 Quintiles Transnational Corp. All rights reserved.

Noven Pharmaceuticals, Inc. STATISTICAL ANALYSIS PLAN: PROTOCOL HP-3070-GL-04 Page 19 of 50

missing intermediate assessments while remaining on study. For primary analysis of the primary endpoint and other efficacy endpoints, missing observations will not be imputed. The primary analysis method for continuous endpoints will be based on a mixed model with repeated measures (MMRM) which utilizes all available data (complete and partial) from subjects included in an analysis set. The MMRM-based approach assumes that data are missing at random (MAR). MAR refers to a missingness mechanism that is independent of missing responses, conditionally on observed response history and covariates. This assumption inherently implies that the treatment effect is similar for those who discontinue prematurely and for those who complete the study in their respective treatment arms.

Sensitivity analyses to investigate robustness to missing data will be performed for the primary endpoint as described in Section 15.1.4, and key secondary endpoint as described in Section 15.2.3.

For analysis of categorical efficacy endpoints, such as PANSS responders based on percent improvement from baseline, subjects discontinuing from the study prematurely or missing intermediate measurements will be considered as non-responders.

Missing safety data will not be imputed.

# 7.4. MULTIPLE COMPARISONS/ MULTIPLICITY

The primary and key secondary efficacy hypotheses will be grouped into two hierarchical families.

- Family 1 is the HP-3070 9mg versus placebo (Hypothesis 1) and the HP-3070 18 mg versus placebo (Hypothesis 2), based on the primary endpoint of change from baseline in PANSS total score at Week 6.
- Family 2 is the HP-3070 9mg versus placebo (Hypothesis 3) and the HP-3070 18 mg versus placebo (Hypothesis 4), based on the key secondary endpoint of change from baseline in CGI-S at Week 6.

A matched parallel gatekeeping procedure (Chen, *et al.*, 2005, Dmitrienko, *et al.*, 2007, Dmitrienko, *et al.*, 2008) will be used to control the overall Type I error rate in a strong sense at the level of 0.05. The hypothesis testing used in this gatekeeping procedure will be based on truncated and regular Hochberg procedure (see Appendix 2 for details) as follows:

- 1. The comparisons for the primary endpoint (hypotheses 1 and 2) are performed using a truncated Hochberg procedure with a truncation parameter  $\gamma$ =0.9.
- 2. The comparisons for CGI-S (hypotheses 3 and 4) corresponding to the doses that were significant in step 1 are performed using a regular Hochberg procedure.

The family F1 serves as a gatekeeper for F2 such that F2 will be examined only when the gatekeeper F1 has been successfully passed (i.e., at least one of the hypotheses in the F1 family is rejected). The matched gatekeeper procedure utilizes the special logical relationship between the primary and the key secondary parameters to enhance the power of statistical testing. The significance in the key secondary endpoint for a dose level cannot be claimed unless its corresponding primary hypothesis is found significant. In other words, the key secondary endpoint can be restricted to the doses where the primary endpoint is significant to account for logical relationships among the multiple comparisons. The subsequent Family will be tested for the hypothesis that corresponds with the dose of the hypothesis in previous Family that demonstrated significant effect over placebo. Multiplicity adjustment will be applied to the analysis of the primary and key secondary endpoints

Document: \\quintiles.net\Enterprise\Apps\sasdata\SASb\SAS\Noven\HP-			
	3070\XWA17541\Biostatistics\Docu	mentation\SAP\Final 6\Noven HP-3070-GL-04 S	AP text Final
	6_18Jan2018.docx		
Author:	[name]	Version Number:	Final 6
		Version Date:	18Jan2018
Template No:	CS TP BS016 – Revision 3	Reference: 0	CS WI BS005

Effective Date: 01May2012

Copyright © 2012 Quintiles Transnational Corp. All rights reserved.

Noven Pharmaceuticals, Inc. STATISTICAL ANALYSIS PLAN: PROTOCOL HP-3070-GL-04 Page 20 of 50

performed on the Full Analysis Set. There will be no multiplicity adjustments made for analysis on the ITT Analysis set or for the other secondary endpoints.

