The study will evaluate 9.0mg (HP-3070 9.0 mg) and 18.0 mg (HP-3070 18.0 mg) of HP-3070 transdermal patches versus placebo transdermal patches. Patches will be applied by site personnel at approximately the same time daily and each patch will be worn for 24 hours. Every day, 24 hours (±15 minutes) after patch application, site personnel will remove previous day's patches and apply new patches.

All subjects will have a follow-up contact (site visit or telephone call, at the discretion of the Investigator) 30 days after the last patch is removed. This contact will be used to collect information about any Adverse Events (AEs) or Serious Adverse Events (SAEs) that may have occurred since discharge and to follow-up on any Adverse Events (AEs) that were on-going at discharge.

Assuming an effect size of 0.35 on the change in PANSS total score from baseline to Week 6 for the two pairwise comparisons between each active HP-3070 treatment arm and placebo, the power for detecting a statistically significant HP-3070 advantage will be approximately 0.90 having 204 evaluable subjects per each treatment arm, using a two-sided alpha level of 0.025 for each comparison. A two-sided overall type I error is equal to 0.05. Having three treatment arms, the total number of subjects randomized in the trial and included in primary analysis set will be approximately 612.

The effect size of 0.35 (difference between means equal to 7 and common standard deviation (SD) equal to 20) was chosen based on the lowest effect size observed in results from the studies conducted with sublingual (SL) asenapine and approved by the Food and Drug Administration (FDA) (Sycrest®/SAPHRIS® [Study 041004, and Study 041023]).

A sample size recalculation (SSR) will be conducted as described in Section 4.2 on the blinded data after approximately 50% of the originally planned number of subjects have been randomized and completed up to 6 weeks of study treatment.

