# APPENDIX 2. MULTIPLICITY ADJUSTMENT: REGULAR AND TRUNCATED HOCHBERG DETAILS

Consider a general problem of testing *m* null hypotheses denoted by  $H_1,...,H_m$ . Let  $p_1,...,p_m$  denote the associated raw (unadjusted) *p*-values. Further, let  $p_{(1)}<...<p_{(m)}$  denote the ordered *p*-values and  $H_{(1)},...,H_{(m)}$  denote the hypotheses corresponding to the ordered *p*-values. Finally, let  $\alpha$  denote the overall Type I error rate.

The regular Hochberg procedure is based on the following testing algorithm:

- Step 1: If  $p_{(m)} > \alpha$ , accept  $H_{(m)}$  and go to Step 2, otherwise reject all null hypotheses and stop.
- Step i = 2,...,m-1: If p(m-i+1) > α/i, accept H(m-i+1) and go to Step i+1, otherwise reject all remaining null hypotheses and stop.
- Step *m*: If  $p_{(1)} > \alpha/m$ , accept  $H_{(1)}$ , otherwise reject  $H_{(1)}$ .

The truncated Hochberg procedure is defined as a convex combination of the Bonferroni procedure and regular Hochberg procedure based on a pre-specified truncation parameter  $0 \le \gamma < 1$  (Dmitrienko, *et al.*; 2008). The truncated Hochberg procedure is based on the following testing algorithm:

- Step 1: If  $p_{(m)} > (\gamma + (1-\gamma)/m)\alpha$ , accept  $H_{(m)}$  and go to Step 2, otherwise reject all null hypotheses and stop.
- Step i = 2,...,m-1: If p(m-i+1) > (γ/i+(1-γ)/m)α, accept H(m-i+1) and go to Step i+1, otherwise reject all remaining null hypotheses and stop.
- Step *m*: If  $p_{(1)} > \alpha/m$ , accept  $H_{(1)}$ , otherwise reject  $H_{(1)}$ .

Document:	\\quintiles.net\Enterprise\Apps\sas	sdata\SASb\SAS\Noven\HP- umentation\SAP\Final 6\Noven HP-3070-GL-04 S	AP text Final
Author:	6_18Jan2018.docx [name]	Version Number:	Final 6
		Version Date:	18Jan2018
Template No:	CS_TP_BS016 – Revision 3	Reference: 0	CS_WI_BS005

Effective Date: 01May2012

Copyright © 2012 Quintiles Transnational Corp. All rights reserved.

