#### Full Analysis Set

This table will be similar to 14.2.1.1.1.

Footnotes will be:

Note: CGI-S = Clinical Global Impression - Severity of Illness Scale, LSM = Least Squares Mean, SE = Standard Error, CI = Confidence Interval, N = number of subjects in the full analysis set by treatment group.

Note: Baseline is defined as the last non-missing measurement taken prior to first dose of double-blind study medication.

Note: CGI-S score is determined by answering the question "Considering your total clinical experience with this particular population, how mentally ill is the subject at this time?" on a scale of 0-7, with 0 indicating not assessed and 7 indicating the most extremely ill subjects.

Note: The mixed linear repeated measures model includes treatment, country, visit, treatment by visit interaction, and baseline value as covariates, and subject as random effect. The correlation of repeated measures within a subject is estimated with an unstructured covariance matrix. The Kenward-Rogers method is used to estimate the denominator degrees of freedom.

Note: Adjusted p-values are calculated according to the Hochberg procedure. Adjustment for multiple comparisons uses a parallel gatekeeping procedure. Adjusted p-values are presented for the secondary endpoint CGI-S Score change from baseline only if at least one of the primary hypotheses for the primary endpoint PANSS total score change from baseline are rejected.

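### When only one dose wins on PANSS, CGI-S is tested at the full 0.05, so the claimed strong 5% error control can rise to about 9% in the worst case

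*SAP*

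**What the plan says.** Section 7.4 groups four hypotheses into two families: PANSS change at Week 6 for 9 mg (H1) and 18 mg (H2), then CGI-S change at Week 6 for 9 mg (H3) and 18 mg (H4). The matched parallel gatekeeping procedure "will be used to control the overall Type I error rate in a strong sense at the level of 0.05". Its parts are:

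- **Step 1.** The PANSS comparisons are "performed using a truncated Hochberg procedure with a truncation parameter" of 0.9.
- **Gate.** Family 2 opens when "at least one of the hypotheses in the F1 family is rejected".
- **Step 2.** The CGI-S comparisons "corresponding to the doses that were significant in step 1 are performed using a regular Hochberg procedure". No significance level is printed for this step.

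Section 7.4 refers to Appendix 2 for the details. Appendix 2 writes both the regular and the truncated Hochberg algorithm in terms of one alpha, introduced there to "denote the overall Type I error rate". It defines no fraction of alpha that carries from Family 1 to Family 2. The general default in section 6.6 is: "All statistical tests of treatment effects will be performed at a 2 sided significance level of 0.05, unless otherwise stated". The footnote to the CGI-S shell, Table 14.2.2.1, says: "Adjusted p-values are calculated according to the Hochberg procedure". It adds that the procedure is a parallel gatekeeping one and that CGI-S adjusted p-values appear only after a PANSS rejection, but it also gives no carried-forward level.

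**The concern.** A truncated Hochberg test gives up a little power on the primary endpoint (0.0475 instead of 0.05 for rejecting both doses). In return, some alpha remains for the next family when one primary hypothesis is not rejected. If Family 2 receives the full 0.05 whether one or both doses win, the truncation serves no purpose and alpha is used twice.

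The harmful case is an ordinary one in a two-dose trial: one dose works on PANSS and the other does not. Two false claims are then possible at once: PANSS for the ineffective dose, and CGI-S for the effective dose if it has no CGI-S effect. Matching CGI-S to the winning dose does not help, because both of these hypotheses are ones the plan allows to be tested.

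At stake is the CGI-S claim after a single-dose win. CGI-S is the only key secondary endpoint, and section 6.6 requires adjusted p-values for it.

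**Working it through.** **Inputs.** From the SAP:

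- overall alpha 0.05 and truncation parameter γ = 0.9 (7.4);
- two hypotheses per family (7.4);
- two-sided tests (6.6);
- 1:1:1 allocation, difference 7, SD 20 and 204 per arm (3.1).

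Equal allocation with a shared placebo arm gives a correlation of 0.5 between the two dose contrasts. The PANSS/CGI-S correlation ρ is not in the SAP. It is an assumption, shown from 0 to 0.9.

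**Design check.** Section 3.1 states that power "will be approximately 0.90 having 204 evaluable subjects per each treatment arm, using a two-sided alpha level of 0.025 for each comparison". The normal formula gives 203 per arm. With 204 per arm, power is 0.902 (normal) or 0.900 (noncentral t). The plan's figure reproduces. The noncentrality is 0.35 × √(204/2) = 3.535.

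**Thresholds from Appendix 2 with m = 2.**

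- Reject both PANSS hypotheses if the larger p ≤ (0.9 + 0.1/2) × 0.05 = 0.0475.
- Otherwise reject the one with the smaller p if that p ≤ 0.05/2 = 0.025.
- Alpha left when one PANSS hypothesis is retained: 0.05 − 0.0475 = 0.0025, which equals (1 − 0.9) × 0.05/2.
- Level the text gives a lone CGI-S test: regular Hochberg on one hypothesis is a single test at 0.05, and 0.05/0.0025 = 20 times what is left.

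**Error in the critical case.** Let H1 be false, and H2 and H3 true. Once H1 is certain to be rejected, a familywise error occurs if p for H2 ≤ 0.0475 or p for H3 ≤ α₂, where α₂ is the level of the CGI-S test.

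- α₂ = 0.05: bound 0.0475 + 0.05 = 0.0975; under independence 1 − 0.9525 × 0.95 = 0.0951.
- α₂ = 0.0025: bound 0.0475 + 0.0025 = 0.0500; under independence 1 − 0.9525 × 0.9975 = 0.0499.

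**Simulation of the whole procedure.** The rows for ρ from 0.3 to 0.9 use 4 million trials per case. In the ρ = 0 row the certain-win values are the exact independence results, and the planned-effect values come from 1 million trials per case.

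| ρ | α₂ = 0.05, certain win | α₂ = 0.05, planned effect | α₂ = 0.0025, certain win | α₂ = 0.0025, planned effect |
|---|---|---|---|---|
| 0 | 9.5% | 8.7% | 5.0% | 4.7% |
| 0.3 | 9.4% | 8.5% | 5.0% | 4.6% |
| 0.5 | 9.4% | 8.1% | 5.0% | 4.6% |
| 0.7 | 9.2% | 7.4% | 5.0% | 4.5% |
| 0.8 | 9.1% | 7.0% | 4.9% | 4.5% |
| 0.9 | 9.0% | 6.7% | 4.9% | 4.5% |

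Here certain win means that the effective dose is always rejected on PANSS, and planned effect means noncentrality 3.535.

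**Alternative reading.** Suppose Family 2 keeps m = 2, so that a lone winning dose is tested at 0.025. The bound is 0.0475 + 0.025 = 0.0725, and the simulated error runs from 5.5% to 7.1% over the same cases. That reading does not restore control either.

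**Where control holds under the text as written.** Under the global null the error is about 4.8%. It is also about 4.8% when both doses are certain to win on PANSS and neither has a CGI-S effect. With both doses at the planned PANSS effect and no CGI-S effect, it is 2.6–4.7% for ρ from 0.9 to 0.

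**The case against.** The strongest reply is that section 7.4 prints no level for step 2, so the full 0.05 is an inference. Appendix 2 sets out the component tests in general terms. The link between the families is named separately, as a matched parallel gatekeeping procedure, and choosing 0.9 makes sense only if leftover alpha is meant to pass on. The authors may well have intended a carried-forward level.

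The premise is right: the 0.05 comes from Appendix 2 and the section 6.6 default. But the SAP sends the reader to Appendix 2 for the rule, and the only alpha there is the overall one. A programmer working from this document would use 0.05. If a smaller level was intended, it is missing from a confirmatory decision rule, and the same sentence is needed.

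The second reply is that 9% is a worst case, and this is correct. It needs one dose sure to win on PANSS, the other null on PANSS, and the winner null on CGI-S. If the winner also works on CGI-S (assumed noncentrality 3), the error is about 4.4%. With both doses at the planned PANSS effect, exactly one wins in only about 7.6% of trials. Strong control, however, is a statement about every configuration, and the SAP claims it.

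Two limits on the concern stand. The PANSS conclusions are not in doubt, since Family 1 on its own is controlled at 0.05. And 0.0025 is the valid level for this γ; another γ, or a fixed split of alpha, could also be made valid.

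**Conclusion.** The rule is wrong as written. Following the SAP, CGI-S for a single winning dose is tested at 0.05 when 0.0025 is available, and the claim of strong control at 0.05 fails. The worst-case familywise error is 9.0–9.5% with a certain PANSS win and 6.7–8.7% at the planned effect. These figures rest on the literal reading of section 7.4 with Appendix 2, a correlation of 0.5 between dose contrasts, and an assumed PANSS/CGI-S correlation of 0 to 0.9. The bound of 0.0975 does not depend on any correlation. The defect is confined to the key secondary claim after a single-dose win, and it must be corrected because that claim depends on the stated control.

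**What to change.** Add to section 7.4 step 2 and to Appendix 2: *Family 2 is tested by the regular Hochberg procedure at α₂ = 0.05 if both H1 and H2 are rejected, and at α₂ = (1 − γ) × 0.05/2 = 0.0025 if exactly one is rejected; otherwise it is not tested.* Define each CGI-S adjusted p-value as the smallest overall alpha at which the complete two-family procedure rejects that hypothesis. Amend the Table 14.2.2.1 footnote, which now names plain Hochberg, to cite this rule. If 0.0025 is judged too strict, a smaller γ would leave more for CGI-S at some cost to PANSS, but it would have to be chosen and justified before unblinding.

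The cost is a short change to the SAP and shells, plus one programmed rule. A CGI-S claim after a single-dose win becomes much harder, which is the real price of the procedure chosen. The change has to be made before unblinding, because afterwards the choice between 0.05 and 0.0025 could itself decide the CGI-S claim.

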# 7.5. EXAMINATION OF SUBGROUPS

Subgroup analyses will be conducted primary and key secondary endpoints on the Full Analysis Set. It should be noted that the study is not designed to detect treatment differences within subgroups.

The following subgroups will be assessed and described within the exploratory analysis sections:

• Gender:

.

- o Female
- o Male
- Age (years):
  - o < 55
  - o ≥55
- Race in 2 categories:
  - Black/African American
  - All other races combined (American Indian/Alaska Native, Asian, Native Hawaiian/Other Pacific Islanders, or White)
- Severity at baseline
  - o < 90 PANSS Total Score

  - $\circ$   $\geq$  90 PANSS Total Score
- Region
  - United States
  - o Russia
  - Rest of World
- BMI  $(kg/m^2)$ 
  - o < 25
  - ≥ 25 to < 30

  - o ≥ 30
- Age of onset (years)
  - o < 25

Document:	ent: \\quintiles.net\Enterprise\Apps\sasdata\SASb\SAS\Noven\HP- 3070\XWA17541\Biostatistics\Documentation\SAP\Final 6\Noven HP-3070-GL-04 SAP text Final 6 18Jan2018.docx		
Author:	[name]	Version Number: Version Date:	Final 6 18Jan2018
Template No:	CS TP BS016 – Revision 3	Reference: C	S WI BS005

Template No: CS\_TP\_BS016 – Revision 3 Effective Date: 01May2012

Copyright © 2012 Quintiles Transnational Corp. All rights reserved.

Additional sub-groups may be added after reviewing the data.

## 8. OUTPUT PRESENTATIONS

Descriptive summaries and statistical analyses will be provided for assessments performed during the doubleblind treatment period and follow-up period. In general, data collected during the screening and single-blind placebo run-in periods will be presented in subject listings only, with the exception of calculated Baseline values which will be summarized and used in analyses as appropriate.

Appendix 1 describes some conventions for presentation of data in outputs.

The templates provided in addition to this SAP will describe the presentations for this study and therefore the format and content of the summary tables, figures and listings to be provided by IQVIA Biostatistics.

#### 9. DISPOSITION AND WITHDRAWALS

All subjects who provide informed consent will be accounted for in this study. Subject disposition will be presented by treatment group and overall, as appropriate.

Number and percentage of subjects randomized will be summarized by country.

Number and percentage of subjects included in each Analysis Set (as defined in Section 5) will be summarized.

Number and percentage of subjects who completed or discontinued the study prematurely will be summarized for the double-blind treatment period overall. Reasons for study discontinuation during the double-blind period will be summarized for the ITT, FAS, safety and PK analysis sets. Reasons for study discontinuations during the single-blind period will be listed for all subjects screened.

A Kaplan-Meier plot of time to discontinuation during the double-blind period will be presented for the ITT analysis set by treatment group, where time-to-event will be computed in days as [date of last dose of double-blind study medication – date of randomization]. For subjects who were randomized but did not receive any double-blind study medication, time-to-event will be equal to 0. Subjects who complete the entire 6 weeks of double-blind treatment will be censored on the date of their last dose of double-blind study medication.

Document:	\\quintiles.net\Enterprise\Apps\sasdata\SASb\SAS\Noven\HP- 3070\XWA17541\Biostatistics\Documentation\SAP\Einal 6\Noven HP-3070-GL-04 SAP text Final		
Author:	6_18Jan2018.docx [name]	Final 6	
		Version Date:	18Jan2018
Template No:	CS TP BS016 – Revision 3	Reference: C	S WI BS005

Effective Date: 01May2012

Copyright © 2012 Quintiles Transnational Corp. All rights reserved.

Noven Pharmaceuticals, Inc. STATISTICAL ANALYSIS PLAN: PROTOCOL HP-3070-GL-04 Page 22 of 50

